In accord with AASLD guidelines, all subjects treated on the protocol (ELAD-treated and Control subjects), will be administered prednisolone/prednisone (40 mg daily) for 7 days unless specifically contraindicated. If steroids are not administered, the rationale for not administering steroids (e.g the specific contraindication) must be documented on the eCRF. After 7 days of prednisolone/prednisone therapy, subjects will be evaluated to assess whether steroid treatment should be continued. Based on clinical judgment and objective measures of clinical response, subjects not responding will be discontinued from steroid treatment and the method used to evaluate the clinical response, and the reason for termination recorded. Care should be exercised in the interpretation of measures such as the Lille score in subjects treated with ELAD due to the impact of extracorporeal therapy on serum bilirubin and prothrombin time. To the extent possible, the same criteria must be applied to both the ELAD-treated and Control subjects to determine continued steroid treatment. If continued use of steroids is judged to be beneficial to the subject, steroid use can be continued for up to 28 days (total). All subjects will stop prednisolone/prednisone 40 mg daily after 28 days of administration unless the Investigator believes that continued use of steroids is warranted. The clinical rationale for extending or stopping steroid dosing must be documented on the eCRFs. If steroid treatment is stopped, a tapering schema may be followed. The recommended tapering schema would take place over 7 days. If an alternative tapering schema is adopted, the rationale for adopting the tapering schema

must be documented. The treatment period of prednisolone/prednisone at 40 mg/day must take into account any prednisolone/prednisone treatment received prior to this hospital admission (e.g., treatment from a transferring hospital).

5.4.1.3 *Standard of Care - Ascites*

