- Status with respect to ventilation, intubation, or need for hemodialysis

In addition the following will be done:

- Vital signs (blood pressure, heart rate, respiration rate, and temperature)
- Blood samples will be obtained for culture ($\times 2$) (See [Section 5.6.1](#))
- Total bilirubin will be obtained and MELD scores will be calculated in accord with [Section 5.2.4](#)

All such procedures and evaluations must be recorded in the appropriate section(s) of the eCRFs.

If the subject is no longer considered eligible, the reason the subject was deemed a Pretreatment Failure will be noted on the appropriate eCRFs. Pretreatment failure in the Control group will result in exclusion from the mITT population.

5.4.3 **Treatment Start**

5.4.3.1 ***ELAD Treatment Start***

Prior to ELAD treatment initiation, subjects will be given 100 mg hydrocortisone (or institutional equivalent) and 50 mg diphenhydramine (or institutional equivalent). The timing for premedication should be in accord with the institution's policy for premedication; if ELAD cartridges need to be replaced premedication does not need to be repeated. Anticoagulation therapy should be considered prior to initiation of ELAD treatment (See [Section 5.5.2.1](#)).

The clinical, laboratory, and hemodynamic assessments will be performed at specified intervals during the study treatment period for both the ELAD and Control groups. An overview of evaluations during study treatment is presented in [Table 2](#) for Control subjects and [Table 3](#) for ELAD subjects.

The Investigator or designee should assess the subject, per their Institutions SOC guidelines for placing a patient on an extracorporeal system, immediately prior to starting the ELAD System blood pump.

All ELAD System management and cartridge placement will be done by ELAD Specialists. Site staff will not be responsible for the management of the ELAD System.

As ELAD may provide some degree of liver function, the dosage of drugs known to be subject to liver metabolism should be carefully monitored by the Investigator or designee in accord with institutional standard of care.

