4.4.2 Severe Alcoholic Hepatitis

Baseline sAH characteristics to be summarized for the ITT population include:

- Steroids >6 weeks prior to baseline (Yes/No); response to steroid treatment (Yes/No/Unknown);
- Steroids during the 6 weeks prior to baseline (Yes/No); response to steroid treatment (Yes/No); and method used to assess response;
- Selected medical treatments at baseline (steroids, pentoxifylline, N-acetyl-cysteine);
- MELD score with corresponding components (creatinine, total bilirubin, and INR);
- Maddrey score with corresponding components (prothrombin time [PT], laboratory control PT, and total bilirubin);
- Subjects that had dialysis at least twice in the past week
- Time from last alcohol consumption to hospital admission (weeks); and
- Time from hospital admission to Randomization (days).

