7.1.4 Assessment of Potential Bias due to Treatment Group Assignment

VTL-308 is an open-label study. While every effort has been made in the study protocol to minimize the effects of post-treatment differences in investigator evaluation, medical care and subject behavior, there is a potential that differences in these factors may be associated with treatment group assignment, and that these differences might influence outcomes. An evaluation of the proportion of survivors at Study Days 28 and 91 will be carried out to determine whether these differences had any impact on study outcome. Parameters assessed will include, but not be limited to, the following:

- Alcohol use post-discharge. This will be evaluated based on either a PEth result of >20 ng/mL (evidence of moderate or heavy alcohol consumption) or any self-report of alcohol use post-discharge (note: a positive PEth result will supersede a self-report of no alcohol use);
- Length of Initial ICU Stay (<Median and ≥Median), defined as the first ICU discharge date minus ICU admission date plus 1, if the admission date is after randomization. If the admission date is before randomization, then the length of stay will be the discharge date minus randomization date plus 1. If the discharge date is missing and the subject died, the death date will be used;
- Length of Initial Hospital Stay (<Median and ≥Median), defined as the hospital discharge date minus randomization date plus 1. If discharge date is missing and the subject died, the death date will be used;
- Steroids Use Post-randomization (Yes/No);
- Steroids Use Post-randomization for <7 days (Yes/No);

- Steroids Use Post-randomization for ≥ 7 to < 14 days (Yes/No);
- Steroids Use Post-randomization for ≥ 14 to < 28 days (Yes/No);
- Steroids Use Post-randomization for at least 28 days (Yes/No);
- Concomitant heparin use within the first 10 days of the study (Yes/No);
- For the ELAD group only, ELAD treatment duration dichotomized based on < 72 hours vs. ≥ 72 hours. This analysis will be based on total ELAD treatment duration inclusive of any time off treatment (i.e., final stop date/time of treatment, defined as the time at which the ultrafiltrate pump is switched off for the last time – initial start date/time of treatment, defined as the time at which the ultrafiltrate pump is switched on for the first time). Additional analyses of ELAD treatment duration are described in [Section 8.2](#) and [8.10.1](#).

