Post-randomization is defined as the steroid starting within one day after Randomization. If start dates are partial/missing for steroid use, the following imputation will be followed:

- If the entire set of steroid dates are partial, and only the year and month are reported, and they are the same year and month as the Randomization date, then the day will be imputed to be the same as the randomization day. If the first steroid date is a complete start date, and the following steroid records have partial dates that are in the same month and year, then all subsequent partial dates will be imputed to be the same as the first steroid date. Otherwise, the day will be imputed to the first day of the month;
- If the entire set of steroid dates are partial, and only the year is reported, and it is the same year as the randomization date, then the day and month will be imputed to be the same as the randomization day and month. If the first steroid date is a complete start date, and the following steroid records have partial dates in the same year, then all subsequent partial dates will be imputed to be the same as the first steroid date. Otherwise, the day and month will be imputed to January 1st;
- If the entire set of steroid dates are completely missing, then the start dates will be imputed to be the same as the randomization date.

The same logic will be applied for steroid end dates, using discontinuation dates instead of randomization dates. If the steroid is ongoing, the last visit date for the subject will be used.

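### SAP 7.1.4 defines post-randomization steroid use by start date alone, so late starters are misclassified and the handling of continuing users is wrong or undefined, within a supportive bias assessment

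*SAP*

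**What the plan says.** SAP 7.1.4 compares survival at Study Days 28 and 91 across features of post-randomization care. Its stated reason is that "there is a potential that differences in these factors may be associated with treatment group assignment, and that these differences might influence outcomes". Five of the listed features concern steroids: any use (Yes/No), and four Yes/No duration bands (under 7 days, 7 to under 14, 14 to under 28, at least 28).

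All five depend on a single sentence: "Post-randomization is defined as the steroid starting within one day after Randomization". It sets no condition on ongoing use, agent or indication. The imputation rules that follow move a wholly partial set of steroid dates to the randomization day when the recorded month and year match randomization. They also set wholly missing start dates to randomization.

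Steroids are standard of care in both arms. Under Protocol 5.4.1.2, all treated subjects "will be administered prednisolone/prednisone (40 mg daily) for 7 days unless specifically contraindicated", and the treatment period "must take into account any prednisolone/prednisone treatment received prior to this hospital admission". SAP 4.4.2 summarizes at baseline "Steroids during the 6 weeks prior to baseline (Yes/No); response to steroid treatment (Yes/No); and method used to assess response". SAP 8.10 lists the subjects who were not on steroids at randomization, with the reason.

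**The concern.** The rule classifies exposure by when a course began, whereas the question in 7.1.4 is who was treated after randomization. The two differ for subjects already on steroids at randomization, whom the protocol and SAP plainly expect, and for subjects who start on day +2 or later.

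If many treated subjects fall in the No row, the comparison of users with non-users loses its meaning and an imbalance between arms could be hidden or created. Protocol 7.3.1 asks the SAP to evaluate differences in standard of care that may affect outcome, and gives steroid administration as an example.

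**Working it through.** The plan states no figure for this variable, so there is nothing to reproduce. The check applies the rule to cases and then sizes the result under stated assumptions.

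**1. Classification.** Strict reading: Yes if the start date minus the randomization date is 0 or 1 day. Looser reading: Yes if that difference is 1 day or less. Each course is taken as one record.

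| Steroid course | 7.1.4 strict | 7.1.4 looser | 8.3.1.1.2 |
|---|---|---|---|
| Began 3 days before randomization, continuing, complete date | No | Yes | unclear |
| Same course, only month and year recorded, both matching randomization | Yes | Yes | unclear |
| Began on the day of randomization | Yes | Yes | Yes |
| Began on day +1 | Yes | Yes | Yes |
| Began on day +2 | No | No | Yes |
| Began on day +5 | No | No | Yes |

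Rows 1 and 2 are the same patient history. On the strict reading, only the completeness of the date changes the code. The last two rows are No on either reading of 7.1.4 but count in 8.3.1.1.2, which considers steroids given for alcoholic hepatitis with a start up to Study Day 28.

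**2. Duration bands.** On the strict reading, a continuing user with a complete date never enters a band. On the looser reading the user enters one, but which one is undefined. Take a course that starts 3 days before randomization and stops 5 days after. Counted from its start it lasts 3 + 5 = 8 days (7 to under 14). Counted from randomization it lasts 5 days (under 7). The same section settles this question for ICU stay: when admission came before randomization, the stay is counted from randomization.

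**3. Possible size (assumptions, not document figures).** Suppose 80% of subjects truly receive steroids after randomization. Of these, a share p began before randomization (20% to 60%) and a share l began after day +1 (5% to 15%). Start dates are complete.

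- Strict: coded Yes = 0.80 × (1 − p − l).
  - p = 0.20, l = 0.05: 0.80 × 0.75 = 0.60. Coded No = 0.40, true users among them = 0.80 − 0.60 = 0.20, share = 0.20/0.40 = 50%.
  - p = 0.60, l = 0.15: 0.80 × 0.25 = 0.20. Coded No = 0.80, true users = 0.60, share = 0.60/0.80 = 75%.
- Looser: coded Yes = 0.80 × (1 − l).
  - l = 0.05: 0.76. Coded No = 0.24, true users = 0.04, share = 0.04/0.24 = 17%.
  - l = 0.15: 0.68. Coded No = 0.32, true users = 0.12, share = 0.12/0.32 = 37.5%.

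**4. ELAD premedication.** Protocol 5.4.3.1 gives ELAD subjects hydrocortisone before treatment starts, and Protocol 8.3.3 records concomitant medications from randomization. SAP 7.3.6 treats End of Study Day 2 as the closest match to ELAD start. Assume a 06:00 morning draw. For randomization between 08:00 and 23:00, End of Study Day 2 falls 46 to 31 hours later, on calendar day +2, outside the window. For randomization between 00:00 and 05:00 it falls 30 to 25 hours later, on day +1, inside a calendar-day window. If 20% of 75 ELAD subjects receive no therapeutic steroid and 0% to 50% of those start ELAD inside the window, the dose alone codes 0 to 75 × 0.20 × 0.50 = 7.5 subjects as Yes. With daytime randomization the lower end is more plausible.

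**The case against.** The strongest reply is that the sentence was probably meant as no later than one day after randomization. Continuing users would then be coded correctly. That is a fair guess at intent, but the SAP does not say it, late starters are still coded No, and the duration gap then opens. A reader might infer that continuing users are miscoded and that the bands also lack a splitting rule. These belong to alternative readings and do not hold together.

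A narrow early window also has a statistical merit. Late starters must survive to start, so pooling them into the Yes row of a survival table would introduce immortal-time bias. This stands, and it rules out simply counting any later steroid as exposure. The SAP does not offer it as a reason, however, and the longer duration bands have the same dependence on survival.

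The window in 8.3.1.1.2 serves a listing about infection risk, so a difference is not wrong in itself. But both places use the term post-randomization, and neither explains the difference.

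A reader might also infer that the trial cannot show whether steroid use was balanced. The documents do not support that. SAP 7.3.3 tabulates survival by use at randomization, during treatment and after treatment. SAP 8.4 summarizes steroids by arm and study period, SAP 8.10 lists those not on steroids at randomization, and SAP 4.3 with Appendix A assesses steroid compliance. None of these repairs the five variables or supplies duration bands.

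Finally, a reader might infer that premedication routinely turns ELAD subjects into steroid users. The timing above shows that the dose usually falls outside the window. Other SAP and protocol text ties steroids to alcoholic hepatitis, and without an indication limit a Control subject given a steroid for another reason would be counted too.

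**Conclusion.** The point holds as a fault in a stated derivation rule. With complete dates, starters from day +2 are non-users under any reading. Continuing users are either misclassified, with the code depending on date completeness, or captured with no rule for their pre-randomization days. The size is unknown. The shares in step 3 rest on the assumed 80%, 20% to 60% and 5% to 15%, none of which the documents give. Premedication is an occasional contributor only.

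The effect is confined to the supportive assessment in 7.1.4. The primary log-rank test, the secondary endpoints and the population definitions do not use these variables. Nor should the point be strengthened by reading Protocol 7.3.1 as ranking steroids as the care difference most likely to affect outcome: it offers them only as an example. The definition should be corrected before the analysis is run.

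**What to change.** In SAP 7.1.4:

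- Define exposure as a steroid given for alcoholic hepatitis that is ongoing at randomization or started within one day after it. The indication limit also keeps the ELAD premedication out.
- Count duration from the later of the start date and randomization, as the section already does for ICU stay.
- Report subjects who start after day +1 in a separate row, with a note or a landmark analysis because they had to survive to start.
- Use the same definition in 7.1.4, 7.3.3 and 8.3.1.1.2, or state why a window differs.

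The cost is SAP text and derivation code. The SAP already relies on steroid start and end dates and on the alcoholic hepatitis indication, so no new data are needed. The small downside is the extra row for late starters, whose survival figures need the caution above.

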Appendix A Standards of Care Compliance Assessment

The questions to assess compliance to the standards of care (SOC) for nutrition, steroids, ascites, gastroesophageal varices, hepatic encephalopathy, hepatorenal syndrome, hyponatremia, spontaneous bacterial peritonitis and hepatic hydrothorax are listed for each medical problem (ascites, gastroesophageal varices, hepatic encephalopathy, hepatorenal syndrome, hyponatremia, spontaneous bacterial peritonitis and hepatic hydrothorax) and both treatment regimens (nutrition and steroids). An overall assessment on subject compliance with each SOC will also be listed.

- Nutrition
 - Did subject have at least one Dietary Consult?
 - Was subject diagnosed with malnutrition?
 - Did subject receive nutritional supplements?
 - Did subject have hypocalcemia, hypomagnesemia, or hypophosphatemia?
 - Did subject receive metal supplements?
 - Did subject have any vitamin deficiencies?
 - Did subject receive vitamin supplements?
 - Overall assessment: was this subject compliant with Nutrition SOC?
- Steroids
 - Did subject receive Prednisone/ Prednisolone for at least 7 days?
 - Was treatment with steroids contraindicated?
 - Overall assessment: was this subject compliant with Steroids SOC?
- Ascites
 - Was subject diagnosed with ascites?
 - Subject underwent a paracentesis if clinically indicated either during screening or after randomization.
 - Ascitic fluid analysis, if clinically indicated, included relevant lab tests (e.g., cell count and differential and if indicated, ascitic fluid cultures)?
 - Diuretics were administered if clinically indicated?
 - Subjects with tense ascites (as assessed by investigator) underwent a paracentesis?
 - Subjects with refractory ascites (as assessed by investigator) underwent a paracentesis followed by oral diuretics?
 - Subjects who had >5 liters of ascitic fluid removed received albumin?

- Overall assessment: was this subject compliant with Ascites SOC?
- Gastroesophageal Varices
 - Was subject diagnosed with gastroesophageal varices?
 - Was the subject diagnosed to have gastroesophageal varices who had no previous history of gastroesophageal bleeding treated with either non-selective beta-blockers, endoscopic venous ligation, endoscopic sclerotherapy, or TIPS?
 - Were subjects who had active bleeding within 2 weeks prior to randomization given an antibiotic?

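### SAP 7.1.4 reuses start-date imputation for partial steroid stop dates, which can give stops before starts and misplaces courses in the duration bands in both directions

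*SAP*

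**What the plan says.** SAP section 7.1.4 examines whether care after randomization differed between the arms of this open-label trial. It tabulates survivors at Days 28 and 91 by several factors, including post-randomization steroid use of under 7 days, 7 to under 14, 14 to under 28, and at least 28 days. Those bands need both a start and a stop date.

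The imputation rules are written for start dates:

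- Month and year known, same month as randomization: "then the day will be imputed to be the same as the randomization day".
- Month and year known, another month: "Otherwise, the day will be imputed to the first day of the month".
- Year only, same year as randomization: "then the day and month will be imputed to be the same as the randomization day and month".
- Year only, another year: "Otherwise, the day and month will be imputed to January 1st".
- Nothing known: "If the entire set of steroid dates are completely missing, then the start dates will be imputed to be the same as the randomization date".
- First record complete, later ones partial in the same month or year: the later dates copy the first.

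Stop dates are covered by one sentence: "The same logic will be applied for steroid end dates, using discontinuation dates instead of randomization dates". Ongoing steroids stop at the last visit date. The SAP does not define the discontinuation date for this purpose.

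**The concern.** The fallbacks (first of the month, 1 January) are the earliest dates compatible with the record. For a stop date they can land before the course began. Suppose steroids start on 10 March, the stop is recorded only as March, and Day 91 is 8 June. The stop becomes 1 March, and the duration is −8 days counted inclusively.

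The other branches push the opposite way. If the stop is completely missing, the same course is given a stop on 8 June and a length of 91 days. A later record with a partial stop can also inherit the first record's stop, which may precede its own start.

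At stake is the reliability of one check. Protocol section 7.3.1 promises that the SAP will examine standard-of-care differences, naming steroids as an example, and the duration bands in 7.1.4 are part of the answer. The result of the rule depends on when the subject discontinues, so any arm difference in early discontinuation or death could carry into the bands.

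**Working it through.** The plan states no figure to reproduce, so the rules were applied directly.

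**Inputs.**

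- Course lengths L: 7 and 28 days, and 35 days for 28 plus the recommended 7-day taper (Protocol 5.4.1.2). Lengths of 14 and 21 days were added.
- Anchor: Study Day 91, the final study day (Protocol 5.4), so discontinuation = randomization + 90 days. That this is what the SAP means is an assumption.
- Randomization: every date in 2016–2017, that is 731 dates in 24 months. This is an assumed calendar; SAP 1.3 gives uniform accrual over at least 720 days.
- Single record, start = randomization, true stop = start + L − 1, duration = stop − start + 1.

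**Day missing, month known.** With Day 91 as anchor and L up to 35, the stop month never equals the discontinuation month, so the stop always becomes the first of the month.

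- The stop precedes the start when the course ends in the month it began and did not begin on the 1st. For L up to 28 that is (731 − 24L)/731.
- A 7-, 14- or 28-day course sits exactly on a band edge. It keeps its band only if the true stop was the 1st: 24/731 = 3.3%.
- A 21- or 35-day course keeps its band if the true stop was on day 1 to 8: 192/731 = 26.3%.

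| True length | Stop before start | Falls to a shorter band |
|---|---|---|
| 7 | 563/731 = 77.0% | 96.7% |
| 14 | 395/731 = 54.0% | 96.7% |
| 21 | 227/731 = 31.1% | 73.7% |
| 28 | 59/731 = 8.1% | 96.7% |
| 35 | 0% | 73.7% |

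The mean duration error is about −14.7 days. Using 720 dates from 1 January 2016 instead gives 77.5%, 54.9% and 8.2% stop-before-start for 7, 14 and 28 days.

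**Earlier discontinuation, 28-day course, day missing.** More stops share the discontinuation month and take that day. The share falling to a shorter band is 6.6% for discontinuation on Day 30, 23.0% on Day 35, 55.8% on Day 45 and 96.7% on Day 60.

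**Year only, Day 91 anchor.** The stop falls in an earlier year than discontinuation for 91 − L dates per year.

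- 7-day: 2 × 84/731 = 23.0% go to 1 January, before the start. The other 77.0% take the discontinuation date and move up to at least 28 days.
- 28-day: 2 × 63/731 = 17.2% go to 1 January, before the start. The other 82.8% stay in the top band.
- If completers are held to have no discontinuation date, every year-only stop becomes 1 January. It then precedes the start in 98.1% of 7-day and 92.3% of 28-day courses.

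**Fully missing, Day 91 anchor.** Every course becomes 91 days and is counted as at least 28.

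**The obvious replacement.** Imputing the last day of the month, capped at discontinuation, gives no stop before start and keeps every 28-day course in band. It moves 77.0% of 7-day and 54.0% of 14-day courses up, with mean error +14.7 days. For year-only stops, 31 December capped at Day 91 gives mean errors of about +57 to +75 days for 7- to 28-day courses.

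**The case against.** The case for leaving the rule alone has several good parts.

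- The 97% depends on course lengths that sit on band edges. A 35-day course gives 74%, and a 5-day course cannot fall to a shorter band at all. This stands, although 7 and 28 days are the lengths the protocol itself uses.
- The figures assume one record per course. If a taper is entered separately and the first record has a complete stop, that stop is not imputed. This stands.
- Partial stops may be rare. Protocol Table 4 requires full documentation of steroid administration and tapering, and recording of post-discharge use through Day 91. SAP section 9 runs edit checks until queries are resolved. This stands; the documents give no rate.

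A reader might infer more than the documents support:

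- *That nearly all 28-day courses would be misbanded.* This ignores the discontinuation-date branch. It holds only for month-only stops with discontinuation around Day 60 or later.
- *That the error falls mainly on long courses.* Band error is the same at 7, 14 and 28 days, and impossible dates are concentrated in short courses.
- *That steroid compliance is also distorted.* Appendix A asks "Did subject receive Prednisone/ Prednisolone for at least 7 days" but does not say that imputed dates will be used to answer it, and SAP 4.3 leaves the method to be developed.
- *That the arms would be affected differently.* This is possible, but nothing in the documents shows it.

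None of this makes a negative duration acceptable.

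**Conclusion.** The rule is wrong as written: a stated derivation can produce stops before starts, and it shortens or lengthens courses according to which part of the date is missing. The size is large within affected records and unknown overall. The percentages rest on Day 91 as the discontinuation date, a single record starting at randomization, and an assumed 2016–2017 calendar.

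The reach is small. Only the exploratory steroid-duration bands in 7.1.4 are affected. The yes/no steroid-use factor is defined by start date, and neither the primary log-rank test nor the secondary endpoints use steroid stop dates. This is a minor correction worth making because it is cheap.

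**What to change.** 1. Define the discontinuation date, including what it means for a subject who completes Day 91.
2. Give stop dates their own rule: each imputed stop lies between that record's start and the earliest of death, study discontinuation or last visit.
3. Classify duration as unknown when the stop is fully missing and the steroid is not recorded as ongoing, or when the earliest and latest possible stops fall in different bands.
4. Show the band tables under earliest possible stops, under latest possible stops, and with imputed records excluded.

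Do not simply switch to last day of the month or 31 December, which reverses the bias.

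The cost is SAP wording, a few lines of derivation code, a few more tables and some subjects labelled unknown. Among month-only stops that label will be common. The latest possible stop never gives a band below the true one, while the earliest gives a lower band in 96.7% of 7-, 14- and 28-day courses in the set-up above, so at least that share become unknown. That reflects what the data can show: a calendar month is at least as wide as any of the closed bands.
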